5.2.1. Minnesota Manual Dexterity Test (MMDT): MMDT measures the speed of gross arm and hand movements (arm-hand dexterity) during rapid eye-hand coordination tasks. The MMDT material consists of a plastic collapsible board with 60 holes and 60 cylindrical blocks (3.7 cm in diameter and 1.9 cm high). The MMDT involve five subtests: Placing Test, Turning Test, Displacing Test, One-hand Turning and Placing Test, and the Two-hand Turning and Placing Test. The Placing Test (1st item: taking the blocks with one hand and putting them in the holes on the board in a standardized order) and Two-hand Turning and Placing Test (5th item: taking the blocks with two hands and putting them in the holes on the board in a standardized order) were the two items selected for this study. Participants were given a 15 second trial for both items. The test was timed with a stopwatch and each item was measured three times. The number of seconds it took to complete the task on each of the trials was recorded. An average score from the three trials was calculated. The high performer should score higher on the MMDT than the low performers.^{8,9}

5.2.2. Video Boxing Analysis (VBA): For boxing analysis patients were videotaped while punching with their right side, punching with side left and punching bilaterally. Than the videotape were watched to analyze and the number of right unilateral punches in 1 minute, number of left unilateral punches in 1 minute and number of bilateral punches in 1 minute were recorded. This analysis were done for the quantitative assessment of punch number per minute (number of punch/minute). This measurement method is created and constructed by the authors of this study. The lower the score, the better the outcome.

5.2.3. Fullerton Advanced Balance (FAB): The FAB scale is a performance-based scale which was developed to evaluate changes in many aspects of balance.¹⁰ The FAB scale consists of 10 test items for the evaluation of static and dynamic balance status. These test items are: 1. Feet together, eyes closed, 2. Reach forward to retrieve an object, 3. Turn in a full circle, 4. Step up and over a bench, 5. Tandem walk, 6. Stand on one leg, 7. Stand on foam, eyes closed, 8. Two-footed jump, 9. Walk with head turns, 10. Reactive postural control. Each test

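### The MMDT is scored in seconds, but the SAP says better performers score higher; the VBA counts punches, but the SAP says lower is better without explanation

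*Combined protocol and SAP*

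**What the plan says.** **MMDT (SAP section 5.2.1).** The test is described as a measure of the speed of arm and hand movement, using a "plastic collapsible board with 60 holes and 60 cylindrical blocks". Two of its five subtests are used, each timed by stopwatch three times. The recorded quantity is explicit: "The number of seconds it took to complete the task on each of the trials was recorded". The score follows from it: "An average score from the three trials was calculated". The next sentence gives the direction: "The high performer should score higher on the MMDT than the low performers".

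**VBA (section 5.2.2).** Right, left and bilateral punches are counted from video over one minute. The direction is then given as "The lower the score, the better the outcome". On the origin of the measure the SAP says: "This measurement method is created and constructed by the authors of this study".

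**Use in the analysis.** Section 5.2 promises the between-group difference in mean change from baseline to 8 weeks, with a 95% confidence interval, for the secondary outcomes. Section 6 reads group differences from p values and confidence intervals together and adds Cohen's d. It sets no convention for the sign of a change or of d.

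**The concern.** A difference in mean change can be read as a benefit for one arm only if the direction of benefit is known. For the MMDT the SAP gives a direction that its own scoring rule rules out. For the VBA it gives one without a reason, and the reader has no cited source to turn to. Each of the two direction sentences would fit the neighbouring measure, so they may have been transposed, but the document does not prove that.

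If the directions are followed as written, the arm that became slower is reported as better on the MMDT and, very probably, the arm throwing fewer punches is reported as better on the VBA. If they are left unresolved, the direction could be settled after the results are known.

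**Working it through.** The plan gives no numerical figure on this point to reproduce. The check compares each instrument's unit with its stated direction and then asks what a reversed sign changes.

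**1. Unit against direction, all instruments**

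| Instrument | Score as defined | Stated direction | Coherent? |
|---|---|---|---|
| WMFT (primary) | Sum of 15 items, 0 to 75 | Lower means less function | Yes |
| MMDT | Mean seconds over three trials | Higher is better | No |
| VBA | Punches per minute | Lower is better | Unexplained |
| FAB | 10 items, 0 to 40 | Higher is better | Yes |
| ACE-R | 0 to 100 | Higher is better | Yes |
| FAI | 15 items, 0 to 45 | Higher is more active | Yes |

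**2. MMDT: seconds to speed**

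Input: 60 blocks (section 5.2.1). The completion times are illustrative.

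Speed in blocks per minute = 60 blocks ÷ (seconds ÷ 60)

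- 90 s: 60 ÷ 1.5 = 40
- 120 s: 60 ÷ 2 = 30
- 150 s: 60 ÷ 2.5 = 24
- 180 s: 60 ÷ 3 = 20

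From 120 s to 180 s the score rises by 60/120 = 50% and the speed falls by 10/30 = 33%. Any fixed number of blocks gives the same direction. The section defines no inversion, rate or block count that would turn a higher score into a better one.

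**3. VBA**

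No arithmetic applies. A count can be declared lower-is-better, and nowhere does the SAP say that more punches is better. The case rests on purpose: a punch count in a trial of boxing training, whose stated aim is to compare effects on upper extremity function, would ordinarily be expected to rise with improvement. The SAP gives no reason for the reverse.

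**4. What a reversed sign changes**

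Inputs: 20 per arm (section 3). The SD of the MMDT change is not in the SAP, so 20 s is assumed.

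95% half-width = t(0.975, 38 df) × SD × √(2/n) = 2.024 × 20 × √(2/20) = 12.8 s

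| Difference in mean change (faster arm minus slower arm) | 95% CI | Cohen's d | Mann-Whitney p |
|---|---|---|---|
| −4.0 s | −16.8 to 8.8 | −0.2 | 0.543 |
| −10.0 s | −22.8 to 2.8 | −0.5 | 0.164 |
| −16.0 s | −28.8 to −3.2 | −0.8 | 0.022 |

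The p values come from constructed normal-score data, so they illustrate and do not predict. Multiplying every change by −1 turns the last row into +16.0 s (3.2 to 28.8) with d = +0.8. The p value, the absolute d and the interval width (2 × 12.8 = 25.6 s) stay the same. Read under higher-is-better, that significant gain in speed becomes a significant loss.

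Other SDs change the precision but not the sign. The half-width is 0.64 × SD, so it is 6.4 s at an SD of 10 s and 19.2 s at 30 s. For a 16 s difference the absolute d is then 16/10 = 1.6 and 16/30 = 0.53.

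**The case against.** **Another reading of the MMDT.** Section 5.2.1 also mentions a 15-second trial for both items and does not say what it is for. If it were a fixed scoring window with blocks counted, higher would be better. But the same paragraph records time to completion, and no block count is defined. The role of those 15 seconds does need a line of explanation. The direction sentence also cites two outside sources that were not available for this review. They could bear on which sentence the authors correct, but the text conflicts with itself whatever they say.

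**The VBA half is inference.** This is fair. The SAP gives an explicit direction for a measure its authors built. The document supports asking them to confirm and justify it; it does not prove an error. The firm count is one instrument of five, with a second very probable.

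**The harm is conditional.** Also fair in part. No one-sided test, responder rule or composite in the SAP depends on direction, and a reader who sees raw seconds may correct the label unaided. That reader must override the plan's own sentence, however, and for the VBA has nothing to check against.

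**The illustration adds little.** The SD and the data are assumed, full retention is assumed, and random samples with the same true effect would give widely varying p values. This stands. The numbers show only that a sign reversal leaves everything but the label unchanged, and the conclusion does not rest on them.

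**Conclusion.** The concern holds and should be fixed. For the MMDT, the score and its stated direction cannot both be right. With a score in seconds, lower is better, and applying the sentence as written names the wrong arm. For the VBA, the stated direction is very probably wrong, but that is a judgement from the purpose of the measure and only the authors can settle it.

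The reach is limited to how benefit is labelled for two of five secondary instruments. The MMDT conclusion assumes only that the task is fixed and that the score is the time the SAP says it is.

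**What to change.** - **Section 5.2.1:** state that the MMDT score is mean seconds to completion and that lower is better. Say what the 15-second trial is for.
- **Section 5.2.2:** state that the VBA score is punches per minute and that higher is better, or have the authors confirm and justify the opposite. Settle this before analysis.
- **Section 6:** state that the direction of benefit will be reported beside each mean change, between-group difference and Cohen's d. Raw seconds can stay as they are; reversing the sign of the MMDT change is optional.

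The cost is one sentence in each of the three sections, a short clarification of the 15-second trial, and one confirmation from the authors. Data collection, tests and sample size do not change.

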- 2. Study design:** In this study participants who had a documented diagnosis of stroke from their neurologist from the local community will be screened for eligibility. The participants who are being diagnosed as first time ever stroke, who has hemiparesis, who are between the ages of 18-70, who has Mini Mental Test score ≥ 23 , whose functional level is less than 4 according to the Modified Rankin Scale and who has upper extremity spasticity < 3 on Modified Ashworth Scale will be included in this study. Individuals will be excluded from the study if they have any of the following criteria: hypertension, heart disease, subluxation and fracture at the shoulder, visual impairment, limitation in passive normal joint movement in hemiplegic side and botulinum toxin administration or surgical operation in the last 6 months. If the participants are eligible to participate they will be randomized to either the virtual boxing group (VBG) or the real boxing group (RBG). Each participant will be randomly assigned to either treatment group with simple randomization (odd - even numbers: odd numbers will represent VBG and even number will represent RBG). The study protocol is presented in *Study protocol - CONSORT diagram* below.
- 3. Sample size calculation:** Sample size will be calculated by using G* Power 3.1.9.2 program. The mean and standard deviation values are taken as a reference from the study of Jo et al.⁴ Statistical power analysis calculations suggested 15 subjects for each group ($\alpha = 0.05$, 95% confidence interval), considering the dropouts the number was increased by 33% and finally 20 subjects planned to be included for each group. Based on the power calculation ($n=20+20$) we will enroll 40 individuals in each treatment group; $n=20$ in virtual boxing group (VBG) and $n=20$ in real boxing group (RBG).

Study protocol (CONSORT diagram)

4. Aims and objectives: To compare the effects of virtual and real boxing training on upper extremity functions (primary outcome measure), cognitive functions, balance functions and activities of daily living (secondary outcome measures) in hemiparetic individuals with stroke.

5. Outcomes: This section will present the outcomes investigated to answer the study aims and objectives.

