5.1. Primary outcome: The primary outcome is Wolf Motor Function Test (WMFT) which quantifies upper extremity motor ability through the use of timed and functional tasks. The original version of the WMFT was developed by Wolf et al in 1989 to examine the patients with moderate to severe upper extremity motor deficits.⁵ Then, the modified version of the test was developed by Taub et al to assess the motor abilities of chronic patients who had suffered mild to moderate stroke.⁶ The widely used version of the WMFT consists of 17 items, items 7 and 14 are related to subject strength and the other 15 to subject functional ability during various tasks. Performances are scored using a 6-point functional ability scale and the less affected upper extremity followed by the most affected side. The total score, also referred to as Functional Ability score (WMFT-FAS), is the sum of the 15 items score (with a 6-point ordinal score from 0 to 5). The maximum

total score is 75, with lower scores indicating lower functional levels.⁷ It will be measured at baseline (0 weeks) and at the completion of the treatment (8 weeks). The change in scores from Baseline to 8 weeks will be calculated.

5.2. Secondary outcomes: Minnesota Manual Dexterity Test (MMDT), Video Boxing Analysis (VBA), Fullerton Advanced Balance (FAB), Addenbrook Cognitive Assessment (ACE-R) and Frenchay Activity Index (FAI). The secondary outcome will be measured at the baseline (0 weeks) and at the completion of the treatment (8 weeks). The change in scores from Baseline to 8 weeks will be calculated. The estimated difference in mean change from baseline to 8 weeks and the corresponding 95 % confidence interval (CI) will be presented.

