The statistical analysis will be carried out using the statistical package SPSS version 24.0. The variables will be reported by percentage (%) and mean \pm standard deviation ($x \pm sd$). Shapiro-Wilk test will be used to determine whether the data had a normal distribution. Pearson’s Chi-Squared Test and Fisher’s Exact Test will be used for comparison of the categorical data between the groups. Mann-Whitney U test will be used to analyze the intergroup differences, and Wilcoxon Signed-Rank Test will be used to analyze the intragroup differences. $P < 0.05$ will be accepted as the statistically significant level. The arithmetic means will be presented with a 95% confidence interval (95% CI) with lower and upper limit values. Both “p” values and 95% CI values will be considered while interpreting the differences between the groups. To analyze the intergroup changes, effect sizes will be calculated with “Cohen’s d”. The effect sizes will be interpreted as small effect ($d \geq 0.2$), medium effect ($d \geq 0.5$) and large effect ($d \geq 0.8$).[30]

The mean difference (MD) will also calculated to evaluate the change from the baseline to post-treatment as mean change \pm standard deviation.

7. References

1. van der Lee JH, Wagenaar RC, Lankhorst GJ, Vogelaar TW, Devillé WL, Bouter LM. Forced Use of the Upper Extremity in Chronic Stroke Patients. *Stroke*. 1999. doi:10.1161/01.str.30.11.2369

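### The unilateral punch counts are defined by right and left, not by affected arm, so each between-group comparison mixes paretic-arm and less-affected-arm effects

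*Combined protocol and SAP*

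**What the plan says.** Section 5.2.2 states that "patients were videotaped while punching with their right side, punching with side left and punching bilaterally", and that three counts were taken from the video: "the number of right unilateral punches in 1 minute, number of left unilateral punches in 1 minute", and a third count of bilateral punches per minute. It describes the measure as created by the study's authors. The section does not mention the affected, paretic or dominant arm.

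Section 2 (Study design) admits patients "diagnosed as first time ever stroke, who has hemiparesis, who are between the ages of 18-70", with no restriction on side. Randomisation is simple and not stratified by side.

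Section 5.2 lists VBA as a secondary outcome and says of the secondary outcomes: "The estimated difference in mean change from baseline to 8 weeks and the corresponding 95 % confidence interval (CI) will be presented". Section 6 adds that the "Mann-Whitney U test will be used to analyze the intergroup differences", with Cohen's d as effect size. It has no recoding, covariate or stratum for side of hemiparesis.

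The plan does refer to side elsewhere. One exclusion in section 2 is "limitation in passive normal joint movement in hemiplegic side", and section 5.1 has the Wolf Motor Function Test (WMFT) done on "the less affected upper extremity followed by the most affected side".

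**The concern.** The stated aim is to compare two trainings on upper extremity function in people with hemiparesis. In such patients the two arms differ in a way that matters, but right and left do not identify which is which: the right arm is the impaired one in some patients and the better one in others. A between-group difference in right punches, or the lack of one, therefore cannot be attributed to either kind of arm.

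Interpretation is the main thing at stake. Power is also at stake if the between-group effect is smaller in the less affected arm, because the larger effect is then diluted. Since VBA is the authors' own measure, this plan holds the only definition of its scoring that the documents give.

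**Working it through.** **The plan's own figures.** There is none for VBA: no effect, SD or side split is given. The only relevant figure is the sample size in section 3: 15 per group raised by 33%, 15 × 1.33 = 19.95, so 20, which agrees with the plan.

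**What a right-count comparison estimates.** Let p be the share of patients whose right arm is paretic, and d_par and d_less the between-group effects on change in each kind of arm. Then

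expected right-count difference = p × d_par + (1 − p) × d_less,

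and the left count has the weights reversed. This is exact for the difference in mean change. Mann-Whitney compares ranks, but of the same mixed distributions.

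**Illustration (all assumed except n and α).** Change scores are normal with SD 1 within each kind of arm, d_par = 0.8, n = 20 per group (section 3), and Mann-Whitney (normal approximation) at 0.05 (section 6), taken as two-sided. There were 40,000 simulated trials per cell, so the Monte Carlo standard error is at most √(0.25/40,000) = 0.25 percentage points.

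Expected differences:
- p = 0.5, d_less = 0: 0.5 × 0.8 + 0.5 × 0 = 0.40
- p = 0.5, d_less = 0.4: 0.40 + 0.20 = 0.60
- p = 0.5, d_less = 0.8: 0.40 + 0.40 = 0.80
- p = 0.3, d_less = 0.4: 0.24 + 0.28 = 0.52
- p = 0.7, d_less = 0.4: 0.56 + 0.12 = 0.68

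Power is 66.9% if the count is coded by affected arm. For right counts at p = 0.5 it is:

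| Change common to both groups | d_less = 0 | d_less = 0.4 | d_less = 0.8 |
|---|---|---|---|
| Same in both kinds of arm | 20.9% | 42.8% | 66.7% |
| 1 SD larger in the less affected arm | 20.2% | 38.3% | 56.6% |
| 1 SD larger in the paretic arm | 15.8% | 33.1% | 56.3% |

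With d_less = 0.4 and the same common change, power is 33.7% at p = 0.3 and 52.3% at p = 0.7.

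The last column shows two things. If both arms respond equally and share the same common change, nothing is lost. If the common change differs by 1 SD, pooling inflates the SD to √(1 + 0.5 × 0.5 × 1²) = 1.118, and the standardised effect falls to 0.8/1.118 = 0.72 although both arms respond equally.

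**Cross-check by formula** (d_less = 0, p = 0.5, same common change). The variance is 1 + 0.25 × 0.8² = 1.16 in one group and 1 in the other, so the average SD is √1.08 = 1.039 and the expected Cohen's d is 0.40/1.039 = 0.385. A normal-approximation test of means then has 22.9% power, against 71.6% for the affected arm. This is the same pattern as the rank test. On the bands in section 6, an effect that is large in the paretic arm (0.8) would be reported as small.

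**Type I error.** With no group effect, p = 0.5, and common change equal or 1, 2 or 3 SD apart between the arms, rejection was 4.9% to 5.0%.

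**Chance imbalance in side.** With p = 0.5 and 20 per group, the probability that the groups differ by at least 4 patients (20 percentage points) in right-sided hemiparesis is 27% (two independent binomial counts). This is ordinary chance imbalance and not bias, but the reader should see it.

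**The case against.** The strongest reply is that section 5.2.2 describes how the video was scored, not how the counts will be analysed. Logging punches by right and left is normal, section 6 names no VBA variable, and nothing forbids recoding. On that reading the plan is merely silent. It is true that recoding is not forbidden. But section 5.2.2 sits among the outcome definitions, and right, left and bilateral are the only forms it gives. Choosing affected-arm coding after seeing results would be an undeclared choice.

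Second, the illustration never lets the less affected arm respond more. That is fair: with effects reversed (paretic 0.4 SD, less affected 0.8 SD, p = 0.5, n = 20), power is about 23% for the affected-arm count, 43% for right counts and 67% for the less-affected-arm count. So recoding does not always raise affected-arm power. It still separates two effects that the right/left counts blend.

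Third, 20 completers per group is favourable. At 15 per group, affected-arm power is 54%, and right counts give about 17%, 34% and 54% for d_less = 0, 0.4 and 0.8. The level falls but the pattern is the same.

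Fourth, a mix of sides is inferred from the absence of a restriction. If nearly all patients had the same affected side, the mixing would largely disappear. The documents also promise no paretic-arm VBA result, and only two of the three counts in one of five secondary outcomes are involved. These points limit the weight of the concern without removing it.

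**Conclusion.** The concern holds. As written, each unilateral VBA comparison estimates a weighted average of paretic-arm and less-affected-arm effects, with weights set by whichever sides the enrolled patients happen to have. That conclusion needs only a sample containing both right and left hemiparesis, which section 2 allows.

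The size is not known. Under the assumptions above (paretic-arm effect 0.8 SD, equal split of sides, 20 per group, same common change in both arms), power falls from about 67% to 43% if the less affected arm shows half the effect and to 21% if it shows none. There is no loss if the two arms behave alike. The harm is to interpretation first, and to power only conditionally. The randomised comparison is unbiased, type I error is nominal, and the WMFT and the bilateral count are not affected. The change is worth making because it is cheap, but the trial's validity does not depend on it. Which arm's WMFT score is primary, and which hand does the Minnesota Placing Test, are separate questions.

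**What to change.** In section 5.2.2, define the two unilateral outcomes as punches per minute with the affected arm and punches per minute with the less affected arm, derived from the recorded right and left counts and each patient's side of hemiparesis. Leave the bilateral count as it is. Add side of hemiparesis by group to the baseline table.

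Date the change in the SAP before any group result is examined. Section 5.2.2 is already written in the past tense, so the timing should be stated openly; if group results have been seen, label the affected-arm analysis post hoc.

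The cost is SAP wording, a recode and one baseline row, with no new measurement. Side should be known for every patient, since an exclusion criterion and the WMFT testing order both depend on it, but this should be confirmed. The drawback is that affected-arm counts pool dominant and non-dominant arms.

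### The between-arm test ignores the baseline scores that are already collected, and WMFT-FAS has no named between-arm estimate whose CI matches the test

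*Combined protocol and SAP*

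**What the plan says.** Section 6 gives one between-arm test for numeric outcomes: "Mann-Whitney U test will be used to analyze the intergroup differences". It names no covariate, model or stratification. A Shapiro-Wilk test is planned, but no parametric between-arm test is listed that its result could lead to.

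Sections 5.1 and 5.2 measure WMFT-FAS and all secondary outcomes at weeks 0 and 8, and both say: "The change in scores from Baseline to 8 weeks will be calculated". Section 6 adds Cohen's d for changes between groups and a mean change with its SD. No sentence links these change scores to the Mann-Whitney test.

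Section 5.2 promises a between-arm estimate with 95% CI for the secondary outcomes: "The estimated difference in mean change from baseline to 8 weeks". Section 5.1 has no such sentence for WMFT-FAS. Section 6 provides 95% CIs for arithmetic means and says that p-values and CIs will be read together when groups are compared. This is general wording, so it covers the primary outcome, but it names no between-arm difference.

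Section 2 states: "Each participant will be randomly assigned to either treatment group with simple randomization". No stratification is described.

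**The concern.** In a trial of 40 people, a baseline value of the outcome is usually the most useful covariate available, and here it is collected for every outcome. The plan uses it at most by subtraction. Subtraction removes too much when the two scores correlate imperfectly. The change score then carries extra noise, and a chance baseline difference is over-corrected. Simple randomisation makes some chance difference likely.

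The second matter is reporting. For the primary outcome the reader would get a p-value from ranks beside CIs and a Cohen's d from means. No between-arm difference in WMFT-FAS is named, and no interval belongs to the test. What is at stake is precision, how a trial with visible baseline imbalance is read, and a clear primary result. The overall validity of the test is not in question.

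**Working it through.** **The plan's own figures.** Section 3: "Statistical power analysis calculations suggested 15 subjects for each group", raised by 33%: 15 × 1.33 = 19.95, so 20 per arm. The 15 cannot be reproduced, because the effect, SD, power and sidedness are not given. For orientation, 15 per arm detects 1.06 SD with 80% power by a two-sided t-test (the 80% is an assumption).

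**Assumed inputs.** Correlation rho between baseline and week 8 of 0.5/0.7/0.85; effects of 0.5, 0.8 and 1.06 SD; equal SDs at both times; normal data; 20 per arm. The SAP gives neither rho nor an effect.

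**Variance of the arm difference**, in units of (2/n) × SD²:
- week-8 score: 1
- change score: 2(1 − rho) = 1.00/0.60/0.30
- ANCOVA: 1 − rho² = 0.75/0.51/0.2775

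Change over ANCOVA = 2/(1 + rho) = 1.33/1.18/1.08. Forty people analysed by change therefore give the precision of ANCOVA on 40(1 + rho)/2 = 30/34/37.

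**Simulated power (%)**, at least 20,000 trials per cell:

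| Effect | Mann-Whitney on change | ANCOVA |
|---|---|---|
| 0.5 SD | 32/49/78 | 42/57/82 |
| 0.8 SD | 67/87/99 | 80/92/99.5 |
| 1.06 SD | 89/98/100 | 96/99.5/100 |

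Part of each gap is ranks against means. Setting ANCOVA against a t-test on change isolates the covariate. It adds about 8/5/2 points at 0.5 SD and about 5 to 6/1/0 at 1.06 SD. If the test were run on week-8 scores instead, power at 0.5 SD would be about 32% at every rho.

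**Unequal arms.** Simple randomisation yields exactly 20:20 in only 12.5% of trials of 40. Simulating it (with a continuity correction in the Mann-Whitney test) gives 31.8/47.5/75.8% v 41.1/56.2/80.2% at 0.5 SD, so the comparison hardly changes.

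**Chance imbalance.** If baseline means differ by D, the expected difference in change is shifted by −(1 − rho)D. One SE of the baseline difference is √(2/20) = 0.316 SD, so the shift at one SE is 0.158/0.095/0.047 SD. Among the 32% of null trials with an imbalance of at least one SE, false positives are 8.8/7.1/6.1% for Mann-Whitney on change and about 5% for ANCOVA. An overall rate of 5% then requires (5 − 0.32 × 8.8)/0.68 = 3.2% in the remaining trials at rho 0.5, and likewise 4.0% and 4.5% at rho 0.7 and 0.85. Direct simulation agrees closely.

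**Test against interval.** At 0.5 SD, the Mann-Whitney p-value and a t-based CI for the difference in mean change disagree about significance in about 6/7/6% of trials.

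**The case against.** The strongest reply is that this is a preference. WMFT-FAS is a bounded sum of ordinal items ("total score is 75, with lower scores indicating lower functional levels"), and a rank test suits such a score, is valid under randomisation and holds its level. That stands. A reader might infer that the planned test is wrong or biased, or that its false-positive rate exceeds 5%. The documents do not support this: the raised rate in imbalanced trials is offset by a lower one in the rest.

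The gain also depends on assumed inputs. At 1.06 SD with rho of 0.7 or more it almost vanishes. That stands too, but the SAP states neither quantity, so it cannot rely on that corner.

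Sections 5 and 6 all lean towards change scores, so the missing link may be a drafting slip. A reader might still infer that the tested score could be picked after the data are seen, which would inflate false positives. The SAP plans no such choice, so no inflation figure belongs here.

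It may be said that section 6 already gives the primary outcome its CIs. It gives mean-based quantities in general terms. It does not name a between-arm difference in WMFT-FAS or an interval that goes with a rank test.

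A ceiling on the 0–75 score might seem to make the loss much larger. The documents give no score distribution, so no weight is placed on that.

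Finally, ANCOVA is not best everywhere. With lognormal residuals (an extreme case), a 0.5 SD effect and rho 0.7, it has 70.2% power, against 84.9% for Mann-Whitney on change and 81.6% for Quade's test. At skewness 1 the disadvantage is nearly gone (58.1% v 54.2% for Mann-Whitney at rho 0.7; 81.9% v 82.4% at rho 0.85). This is a reason to keep a rank-based analysis alongside.

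**Conclusion.** The point holds as a recommended improvement. The unadjusted Mann-Whitney test is valid but gives up precision that the collected baselines would supply: 8% to 33% more variance on change scores than with ANCOVA for rho from 0.85 down to 0.5. For a 0.5 SD effect, moving to ANCOVA adds about 10/8/4 points of power, most of it from the covariate at rho 0.5 and 0.7 and about half at 0.85. In the third of trials with at least one SE of baseline imbalance, false positives are about 9/7/6% instead of 5%, balanced by roughly 3 to 4.5% elsewhere. All of this assumes normal data, 20 per arm and the stated correlations.

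Two gaps rest on the text alone and stand whichever test is preferred: the tested score is not stated, and WMFT-FAS has no named between-arm estimate with a CI that matches the test.

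**What to change.** Prespecify for the primary outcome:

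> Week-8 WMFT-FAS will be compared between arms by ANCOVA with arm as factor and baseline WMFT-FAS as covariate; the adjusted mean difference, 95% CI and p-value all come from this model.

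Use the same model for each secondary outcome with its own baseline. Completion times and punch counts may need a transformation; name it before the arms are compared. Name one rank-based sensitivity analysis in advance: Quade's rank ANCOVA. If the Mann-Whitney test stays primary, state that it is applied to change scores and report the Hodges-Lehmann shift with 95% CI.

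The cost is a few sentences and one linear model per outcome, with no new measurements. The downside is lower power than a rank test if residuals are strongly skewed, which the sensitivity analysis is there to show. Section 5.2.1 describes measurement in the past tense ("The number of seconds it took to complete the task on each of the trials was recorded"), so data collection may have begun, although this is an inference. In that case, date the change and make it before the arms are compared.
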